### 13.7 Safety Assessment

The number and proportion of participants with adverse events in two groups were described and were evaluated by using Chi-squared test or Fisher's exact probabilities. The number and proportion of participants with intervention-related adversre events were described.

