# 2.4.8 Safety Assessment

## 2.4.8.1 Adverse Events

The adverse events are some unintended symptoms, physical signs, or health conditions that show up during the whole trial. They may or may not have causality with the interventions. A health condition or an illness existing before the trial can be deemed as an adverse event (AE) if the situation becomes worse within the study period. An abnormal result of the laboratory examination can be deemed as an AE only if it causes some clinical symptoms and/or require related treatments. We will look for adverse events by asking the participants non-inducing questions at each assessing point. We will also look for the adverse events through participants' self-report, or through physical examination, or by laboratory examination. All the adverse events must be recorded at length on the CRF. If an AE was observed, the following information should be acquired:

- 1. Degree of severity (mild, moderate, severe);
- 2. If it is related to the interventions (affirmably, very likely, possibly, possibly not, affirmably not);
- 3. Duration of the AE (start and end dates, whether still exists at the end of the trial);
- 4. Severe adverse effect (SAE) or not.

SAE is defined as any of the following:

- 1. Fatal or life threatening;
- 2. Permanent or loss of function or disability;
- 3. Need hospitalization or need prolonged hospitalization;
- 4. Severe medical accidents, which need medical or surgical interventions to prevent any of the above occurs.

Solution for controlling the adverse events:

Observation, without any treatment;

Adjusting or stopping the treatment;

Aborting the trial permanently;

Adding combined drugs therapy;

Giving non-pharmacologic therapy;

Hospitalizing or prolonging hospitalization.

All the treatment measures for the adverse events should be recorded in detail on the CRF. We will follow up with the adverse event through the whole trial until its resolution. We will confirm if it is permanent. At every assessing point, we will evaluate the adverse event's severity, relation to our interventions, and arrange appropriate the treatments. The common adverse events related to the interventions are listed in the investigator's brochure. To update the brochure, related adverse events will be announced by the form of investigator's note (IN). We will also discuss with the participants about the adverse events that might occur during the trial.

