# 2.4.8.3 Safety and Acceptance Evaluation

The adverse events should be documented in detail over the treatment and follow-up periods. Participants and

acupuncturists will be responsible for recording adverse events.

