#### 7.3 Prucalopride Group

Prucalopride Succinate (Janssen S.P.A) will be taken orally at a dose of 2 mg/day before breakfast for 8 weeks. Participants will undergo an electrocardiogram (ECG) at the 8th week, and the drug will be taken for another 24 weeks in the absence of QT interval elongation or other severe cardiac adverse events (like myocardial infarction, severe arrhythmia, etc.). The use of other medicine for constipation will not be allowed during the trial. Prucalopride will be distributed to the participants beforehand every 2 weeks in the treatment period, and every 4 weeks in the follow-up period. The untaken pills will be recycled on the day of next distribution.

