#### 10.3 Secondary Outcomes

- 1) The proportion of participants with 3 or more mean weekly CSBMs over weeks 1-2, 11-12, 15-16, 19-20, 31-32. The EA group was discontinued after 8 weeks of treatment, while the drug group continued to take prucalopride for 24 weeks in the absence of QT interval elongation or other severe cardiac adverse events (like myocardial infarction, severe arrhythmia, etc.). Assessing time frame: weeks 1-2, weeks 11-12, 15-16, 19-20, 31-32
- 2) The proportion of participants with  $\geq 1$  increase of mean weekly CSBMs from baseline over weeks 1-2, 3-8, 11-12, 15-16, 19-20, 31-32. Assessing time frame: baseline, weeks 1-2, weeks 3-8, weeks 11-12, 15-16, 19-20, 31-32.
- 3) The change from baseline in mean weekly CSBMs over weeks 1-2, 3-8, 11-12, 15-16, 19-20, 31-32. Assessing time frame: baseline, weeks 1-2, weeks 3-8, weeks 11-12, 15-16, 19-20, 31-32.
- 4) The change from baseline in mean weekly SBMs over weeks 1-2, 3-8, 11-12, 15-16, 19-20, 31-32. Assessing time: baseline, weeks 1-2, weeks 3-8, weeks 11-12, 15-16, 19-20, 31-32.
- 5) The change from baseline in the mean score of stool consistency of each SBM over weeks 1-2 and weeks 3-8. Assessing time: baseline, weeks 1-2 and weeks 3-8. Participants will self-report their stool consistency of each SBM according to the 7-type BSFS (scored by 1 to 7 respectively).

- Type 1: Separate hard lumps, like nuts (hard to pass)
- Type 2: Sausage-shaped, but lumpy
- Type 3: Like a sausage but with cracks on its surface
- Type 4: Like a sausage or snake, smooth and soft
- Type 5: Soft blobs with clear cut edges (passed easily)
- Type 6: Fluffy pieces with ragged edges, a mushy stool
- Type 7: Watery, no solid pieces. Entirely liquidz
- 6) The change from baseline in the mean score of straining of each SBM over weeks 1-2, weeks 3-8, weeks 11-12, 15-16, 19-20, 31-32. Assessing time: baseline, weeks 1-2, 3-8, 11-12, 15-16, 19-20, 31-32. Participants will self-report their straining degree of each SBM in the defecation diaries according to the following scale:
  - 0 = not difficult;
  - 1 = a little difficult, need some straining to defecate;
  - 2 = difficult, need straining to defecate;
  - 3 = very difficult, need hard straining to defecate.

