### 11. Safety and Acceptance Evaluation

# 11.1 Adverse Events

The adverse events are some unintended symptoms, physical signs, or health conditions that show up during the whole trial. They may have no causality with the interventions. A health condition or an illness existing before the trial can be deemed as an adverse event (AE) if the situation becomes worse within the study period. An abnormal result of the laboratory examination can be deemed as an AE only if it causes some clinical symptoms and need related therapies. We observe the adverse events by asking the participants non-inducing questions at each assessing point. We also observe the adverse events through participants' self-report, or through physical examination, or by laboratory examination. All the adverse events must be record at length on the CRF.

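### The single between-arm adverse event test in SAP 13.7 has no time window, so it compares 8 weeks of EA with up to 32 weeks of prucalopride and cannot separate tolerability from length of treatment

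*Supplement*

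**What the plan says.** **The test.** SAP 13.7 reads: "The number and proportion of participants with adverse events in two groups were described and were evaluated by using Chi-squared test", with Fisher's exact test as the alternative. Its only other sentence is "The number and proportion of participants with intervention-related adversre events were described", which is a description without a test. Neither sentence gives a window, an on-treatment restriction or an exposure adjustment. Most items in SAP 13.6, by contrast, state a timeframe or time point.

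**The window that applies by default.** SAP 11.1 gives the definition: "The adverse events are some unintended symptoms, physical signs, or health conditions that show up during the whole trial". Final protocol 2.4.8.3 adds: "The adverse events should be documented in detail over the treatment and follow-up periods". SAP 8 sets those periods at weeks 1-8 and weeks 9-32.

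**Exposure.** SAP 7.2 gives EA as 28 sessions over 8 weeks. For prucalopride, SAP 7.3 says that after the first 8 weeks "the drug will be taken for another 24 weeks in the absence of QT interval elongation" or other severe cardiac events. SAP 10.3 item 1 acknowledges the difference: "The EA group was discontinued after 8 weeks of treatment", while the drug arm goes on.

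**Onset dates.** Final protocol 2.4.8.1 requires, for each event, "Duration of the AE (start and end dates, whether still exists at the end of the trial". Final protocol 2.4.8.2 mentions a decision on whether events are treatment-emergent, but it defines no window and SAP 13.7 does not use the term.

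**The concern.** In weeks 9-32 one arm may be on active drug and the other has no trial treatment. A participant whose first drug-related event falls in those weeks counts against prucalopride, and the EA arm has no matching exposure. Two treatments that are equally well tolerated while given could therefore show different proportions simply because one is given for longer.

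This matters because comparing the safety of EA and prucalopride is a stated aim (SAP 2, final protocol 2.2), and this is the only safety comparison that is tested. A significant result could be reported as better tolerability when the test cannot distinguish that from a shorter course.

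**Working it through.** **1. Inputs from the documents**
- Treated time: 8 weeks for EA (SAP 7.2) and up to 8 + 24 = 32 weeks for prucalopride (SAP 7.3), a ratio of up to 4:1.
- Follow-up: 32 weeks from randomisation in both arms (SAP 8).
- Safety test: two-sided at 0.05 (SAP 13.3).
- Size: 560 participants (SAP 9), allocated 1:1 (SAP 4), so 280 per arm.

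**2. The plan's own figure.** The plan gives no adverse event rate and no power for the safety test. Its sample size, used here only to fix n, reproduces: (1.645 + 0.845)² × [0.3167 × 0.6833 + 0.309 × 0.691] / 0.1077² = 229.8, rounded up to 230, and 230 × 1.2 = 276. The recruitment target raises this to 280 per arm.

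**3. Assumptions, not from the documents.** The weekly hazard h of a first event is constant and the same in both arms while treated. After week 8 the EA hazard is r × h. The eight-week risk is 10% in both arms, so h = −ln(0.90)/8 = 0.01317 per week.

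**4. Formulas**
- Prucalopride by week 32: 1 − exp(−32h) = 1 − 0.90⁴ = 34.4%.
- EA by week 32: 1 − exp(−h(8 + 24r)).
- Chance of p<0.05: Φ[(d − 1.96·SE₀)/SE₁], where d is the difference in proportions, SE₀ the pooled and SE₁ the unpooled standard error.

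Worked case, r = 0.5: EA = 1 − 0.90^2.5 = 23.2%, d = 0.1123, SE₀ = 0.0383, SE₁ = 0.0380. The result is Φ(0.98) = 84%.

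**5. Results, 280 per arm, equal tolerability while treated**

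| r (off/on hazard) | EA, 32 weeks | Prucalopride, 32 weeks | Chance of p<0.05 |
|---|---|---|---|
| 0 | 10.0% | 34.4% | >99% |
| 0.25 | 16.8% | 34.4% | >99% |
| 0.5 | 23.2% | 34.4% | 84% |
| 0.75 | 29.0% | 34.4% | 28% |
| 1 | 34.4% | 34.4% | 5% (nominal level) |

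At r = 0.5, varying the eight-week risk from 5% to 30% moves the chance from 57% to 99%. With 230 rather than 280 per arm, the 84% becomes 76%.

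**6. If events come early.** Take 10% by week 8 in both arms and no later events on EA. An extra first-onset risk on drug in weeks 9-32 of 2%, 5% or 10% among those still event-free gives prucalopride totals of 11.8%, 14.5% or 19.0%. The chance of p<0.05 is then 10%, 37% or 86%. With no late events it is 5%.

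**7. Restricting to weeks 1-8.** Under the same assumptions the risks are 10% in both arms, and the test rejects at its nominal 5%.

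**The case against.** **The whole-period comparison is legitimate.** Both arms have the same planned calendar follow-up, and the randomised strategies are 8 weeks of EA then nothing, against up to 32 weeks of drug. Fewer participants with events under the shorter strategy would be a real difference between strategies. This stands, and it is why the analysis should be kept. But the SAP does not label it so, and it cannot also serve as the comparison of tolerability.

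**The 32-week window is inferred.** SAP 13.7 does not state it. It follows from the definition in SAP 11.1, the recording rule in the protocol, and the absence of any other window. That is the natural reading, but it is a reading.

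**Some features could offset the tendency.** EA participants attend 28 sessions at which acupuncturists record a long list of events, including minor ones (SAP 11.1), which may raise the EA count in weeks 1-8. Worsening of a pre-existing condition can count as an event, so returning symptoms after EA stops could add late EA events. Continued drug is conditional and 20% dropout is allowed for, so 32 weeks and 280 per arm are upper limits. These points affect size, and none removes the difference in exposure.

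**Two stronger readings are tempting.** A reader might infer that a significant result for EA is close to guaranteed. The documents give no adverse event rates, and plausible assumptions put the chance anywhere from 5% to over 99%. A reader might also infer that efficacy and safety cover different periods and cannot be set side by side. Only the primary outcome is confined to weeks 3-8: SAP 10.3 and 13.6 compare efficacy between arms through weeks 31-32, and persistence of the EA effect is a stated objective.

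**Conclusion.** The point holds as a fault in the choice of analysis. Applied as written, the sole between-arm safety test confounds tolerability with a planned treatment length that differs up to fourfold, and it tends to favour EA. No part of the latest protocol or SAP splits adverse events at week 8 or adjusts for exposure.

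The direction rests on the design, with the offsets noted. The magnitude rests wholly on assumed rates: large if on-treatment risk persists and falls once treatment stops, small if drug events cluster in the first weeks, and nil if risk off treatment equals risk on treatment. The primary outcome is untouched. The change should be made because it bears on a stated aim and on a safety statement likely to be prominent in the report.

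**What to change.** Amend SAP 13.7 in three parts:
1. Add a between-arm comparison of participants with an adverse event whose onset falls in weeks 1-8, when both arms are under treatment, with the risk difference and its 95% CI.
2. Report events with onset in weeks 9-32 separately by arm.
3. Keep the whole-period comparison, state that it covers weeks 1-32, label it as a comparison of treatment strategies, and give exposure time per arm beside it.

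The cost is low: start dates are already required, so this means extra tables and no new data or change in conduct. The drawback is that weeks 1-8 contain fewer events, so that comparison is less precise. It also does not correct for closer recording in the EA arm, which should be mentioned when the result is interpreted.
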